7.1 Treatments to be administered

Finerenone immediate-release (IR) tablets are light orange film-coated tablets, oval (modified oblong), containing 10 mg or 20 mg finerenone (Table 7-1). Matching placebo tablets will be supplied.

Following a Screening Visit, eligible subjects will be randomized 1:1 to either finerenone or placebo, and study drug will be dispensed according to the visit schedule (see Section 9.1).

The subject will receive the following:

- Finerenone
 - 10 mg finerenone tablet once daily (OD)
(starting dose for subjects with an eGFR between 25 to < 60 mL/min/1.73m² at the Screening Visit)
 - 20 mg finerenone tablet OD
(starting dose for subjects with an eGFR ≥ 60 mL/min/1.73m² at the Screening Visit)

or

- Placebo tablet OD.

Following randomization of the subject, the IxRS will determine the bottle number for the study site investigator or designee to select for the subject. The investigator at the study site is to instruct subjects to take 1 tablet OD, preferably in the morning. The first dose of study drug should be taken at the site on the same day as Visit 1 (Day 1), preferably in the morning.

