9.2.3 Visit 1 (randomization; Day 1 and baseline) - *amended*

This section was changed in Amendment 3, see Section 15.1.2.16.

All measurements on Visit 1 are to be performed on the day of the visit before first study drug intake. The following procedures and assessments will be performed at Visit 1:

- Instruct the subject on how to complete KDQOL-36 and EQ-5D-5L questionnaires; the subject completes the questionnaires (see Section 9.7.7).
- Obtain informed consent for sub-studies (see Section 9.7.8.1)
- Check inclusion and exclusion criteria (see Sections 6.1 and 6.2)

- Record use of concomitant medication (see Section 8.1)
- Record body weight (see Section 9.7.4)
- Record vital signs (see Section 9.7.5)
- Perform 12-lead ECG (see Section 9.7.6)
- Take samples (hematology, HbA_{1c}, chemistry, urinalysis) for central laboratory evaluations (see Section 9.7.2.1)
- Take samples (potassium, creatinine) for local safety laboratory evaluations (see Section 9.7.2.2)
- Optional: if the subject had signed informed consent for the sub-study, obtain respective samples for biomarkers (see Section 9.7.8.1.2) and/or iohexol clearance (see Section 9.7.8.1.3), perform echocardiography (see Section 9.7.8.1.1)
Note: Time window for the echocardiography at Visit 1 is -14/+7 days. On the day the echocardiography is performed, a blood sample should also be drawn to assess the echo biomarkers.
- Randomization to finerenone or placebo once daily (see Section 7.1)
- Dispense the study drug (see Section 7.2)
- Record adverse events (see Section 9.6.1), accounting for the rules of assessment and documentation (see Section 9.6.1.3)
- First administration of study drug.

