The derived visit '*Any time post baseline*' (applicable for efficacy) will include any measurement after randomization, including unscheduled assessments. For the derived visit '*Any time on treatment*', only assessments up to 30 days after last study drug administration, including unscheduled assessments, will be considered (applicable for efficacy; for safety assessments within 3 days after last study drug administration will be considered).

Further details on the statistical analyses will be provided in the SAP that will be approved before database release.

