10.3.4.2 Laboratory data

The number of subjects with treatment emergent (until 3 days after any temporary or permanent interruption of study drug) abnormal laboratory values above or below the normal range will be tabulated by the laboratory parameter and treatment group.

Summary statistics including changes to baseline will be calculated by treatment group and visit for all quantitative laboratory parameters, e.g. for hematology, HbA1c, clinical chemistry and urinalysis. Geometric statistics and ratios to baseline will be presented for creatinine

instead of arithmetic statistics with changes from baseline. For eGFR the relative change will be displayed in addition to the absolute change from baseline.

Summary statistics for serum potassium, eGFR and serum creatinine will also be repeated by treatment group and visit separately for each level of the stratification factors (type of albuminuria, region and eGFR category).

The following special safety parameters will be further assessed by displaying the number of subjects with safety events as described below by treatment group, visit and for any time on treatment (including unscheduled assessments) and up to 3 days after last study drug administration. This will also be performed by stratification factors. The summaries will be performed for the number of subjects with

- Absolute value of serum potassium >5.5 mmol/L and >6 mmol/L
- Relative decrease from baseline in eGFR of $\geq 30\%$, $\geq 40\%$, $\geq 50\%$ and $\geq 57\%$, also sustained decrease over 4 weeks
- Absolute value of eGFR < 30 mL/min/1.73m²

The percentage of subjects with the respective events (non-stratified) at any time post-baseline (including unscheduled assessments) and within 3 days after last study drug administration will be compared between the finerenone and the placebo treatment group by applying separate explorative χ^2 tests with continuity correction. If the expected number of subjects in at least 1 cell of the 2x2 contingency table is <5 (51), Fisher's exact test will be applied instead of the χ^2 test. Estimates and two-sided 95% confidence intervals will be provided for each treatment group and the treatment differences. Clopper Pearson confidence intervals will be calculated for each treatment group, while for treatment differences the exact unconditional confidence limits will be calculated.

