4.5.1 Baseline values

Baseline values will be defined as the last non-missing measurement before or on the day of randomization. If the last observation available prior to randomization is the measurement from the Screening Visit, this would be used as the baseline value. This also includes assessments from a local laboratory, in case that prior to randomization, no assessment from the central laboratory is available. Otherwise baseline will be missing. The measurement from the Run-in Visit will not be used as a baseline value unless otherwise specified.

If more than one measurement was planned for a scheduled visit, for example blood pressure measurements and heart rate, the mean value of these measurements per time point prior to randomization will be used as the baseline value.

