4.5.3 Other data handling

Only the data provided by the central laboratory will be used for analysis, values from local laboratories will not be used in the statistical analysis and will be listed only unless there are no values from the central laboratory available for baseline.

In case of retests for Run-in and Screening visits, the closest measurement prior to randomization will be used for analysis instead of the scheduled measurements. At all visits starting at Visit 1 and if not stated otherwise, only the values at scheduled measurements will be used for analysis. In the unexpected case that more values than planned are available for a scheduled visit, only the first valid value will be used.

For the derived visit “Any time post-baseline” (applicable for efficacy) this will include any measurement after date of randomization, including unscheduled assessments. For the derived visit “Any treatment-emergent” (applicable for safety), only assessments on or after study medication start date until 3 days after the date of any temporary or permanent interruption of study drug, including unscheduled assessments, will be considered.

For those laboratory values which are <LLOQ (Lower limit of quantification), half the value of the LLOQ will be used for analysis. Differences between 2 values <LLOQ will be assigned values of 0. Ratios between 2 values <LLOQ will be assigned a value of 1. For values which are >ULOQ (Upper limit of quantification), the ULOQ will be used for analysis. This rule does not apply to the finerenone plasma concentration data.

In case of log-normally distributed data, descriptive statistics other than minimum, maximum and median will only be calculated if at least 2/3 of the individual data were measured and were above the lower limit of quantification. In tables showing descriptive statistics, where values below LLOQ are included, these descriptive statistics will be marked.

Urinalysis is assessed 3 times per visit. UACR will be determined 3 times at each visit from first morning void urine samples collected on 3 consecutive days. For the analyses of UACR, the 3 measurements at one visit will be combined provided that at least 2 measurements are available. First, the coefficient of variation (CV) will be calculated for the 3 values as follows considering the log-normal distribution for UACR [7]:

$$CV = \sqrt{\exp(SD_{ln}^2) - 1},$$

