6.4.1 Adverse events

Adverse events (AEs) will be coded using the Medical Dictionary for Regulatory Activities (MedDRA, latest version available prior to data base freeze). A listing will be provided linking the original investigator terms and the coded terms. AEs will also be presented grouped by SMQs.

AEs that started or worsened after the first dose of study drug up to 3 days after any temporary or permanent interruption of study drug will be considered as treatment-emergent AEs (TEAEs).

An overall summary of all AEs and TEAEs will be generated by treatment group.

The number of subjects with TEAEs, pre-randomization AEs, post-treatment AEs occurring more than 3 days after any temporary or permanent stop of study drug, treatment-emergent SAEs, treatment-emergent study drug-related AEs, treatment-emergent study drug-related SAEs, treatment-emergent SAEs and TEAEs causing permanent discontinuation of study drug, treatment-emergent non-serious AEs, non-serious AEs, TEAEs by maximum intensity, treatment-emergent SAEs by maximum intensity, drug-related TEAEs by maximum intensity, TEAEs by worst outcome and treatment-emergent SAEs by worst outcome will be summarized by treatment group using MedDRA terms grouped by Primary System Organ Class and Preferred Term.

To comply with local regulatory requirements in Japan, some cardiovascular disease-related outcome events will also be documented as (S)AEs in Japan. These will be included in the outcome event tables (see section 6.2.3.6), and to avoid double-counting of such events, they will not be included in the adverse event summary tables or listings. A separate listing will be generated for all AEs excluded from the AE analysis due to double reporting in Japan.

In case of events with different intensity within a subject, the maximum reported intensity will be used. If intensity is missing, the event will be considered as severe. If the same event is considered as both unrelated and related to the study drug within a subject, the event will be reported as related to study drug. If the drug relationship is missing, the event will be considered as being related to the study drug.

These further safety variables are listed in section 10.3.4 of the protocol:

- Number of subjects with hospitalization for hyperkalemia
- Number of subjects discontinuing study drug permanently due to hyperkalemia
- Number of subjects with hospitalization for worsening of renal function

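### Pre-dose status is counted as treatment-emergent: the SAP safety window admits the Visit 1 baseline sample, and eGFR <30 has no baseline condition although entry is allowed from 25

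*SAP*

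**What the plan says.** **Window.** SAP 4.5.3 defines the derived visit *Any treatment-emergent*, used for safety, as "only assessments on or after study medication start date until 3 days after the date of any temporary or permanent interruption of study drug". The rule works on dates, and the start date itself is inside.

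**Visit 1.** Protocol 9.2.3 says: "All measurements on Visit 1 are to be performed on the day of the visit before first study drug intake". Those measurements include central chemistry. Protocol 7.1 puts the first dose at the site on that same day, and SAP 4.3 expects the same. SAP 4.5.1 then says: "Baseline values will be defined as the last non-missing measurement before or on the day of randomization".

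**Other windows, for contrast.** The efficacy window in the same paragraph of SAP 4.5.3 starts after the randomization date. SAP 6.4.1 limits treatment-emergent adverse events to "AEs that started or worsened after the first dose of study drug" (up to 3 days after an interruption). Protocol 10.3.4.2 set the between-arm laboratory comparison as "The percentage of subjects with the respective events (non-stratified) at any time post-baseline". The protocol's on-treatment definition in 10.1 ("for safety assessments within 3 days after last study drug administration will be considered") sets only an upper limit, so it does not conflict with the SAP on this point.

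**Threshold.** Protocol 10.3.4.2 lists "Absolute value of eGFR < 30 mL/min/1.73m²" as a special safety event. SAP 6.4.2 keeps it under the treatment-emergent label. Neither places a condition on baseline. SAP 6.4.2 compares the arms with a non-stratified, explorative chi-square test with continuity correction and gives 95% confidence intervals. Protocol 6.1 allows entry from eGFR 25 in both albuminuria groups, and the subgroup list in SAP 4.5.4 includes a baseline category below 25.

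**The concern.** There are two separate faults.

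1. For every patient dosed on the day of Visit 1, which is the plan for all, one blood sample is both the baseline and a treatment-emergent value. A value measured before any drug cannot have emerged on drug.
2. Even with that sample removed, a patient who enters at 25 to <30 becomes an event at the first on-drug sample below 30, without any change.

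Randomization balances the pre-existing cases between arms, so type I error is not inflated and neither arm is favoured. The effect is dilution: both rates rise by the same mechanism, and the difference and ratio move toward no difference. For a drug whose renal safety is under scrutiny, that is the unhelpful direction.

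The effect is mainly on eGFR <30. For potassium >5.5 mmol/L it is probably small, because entry requires ≤4.8 at Run-in and Screening. Relative eGFR declines are unaffected where Visit 1 is the baseline, since that value has zero change from itself.

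**Working it through.** The plan states no figure on this point, so there is nothing to reproduce. The faults follow from the text; the arithmetic only shows their size.

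**Inputs from the documents**
- Entry eGFR from 25 (Protocol 6.1).
- Caps of about 10% on high albuminuria, and about 10% of the very-high-albuminuria group at eGFR ≥60 (Protocol 7.3).
- About 5800 randomized (SAP section 3), so 2900 per arm.

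**Assumed**
- Uniform spread of eGFR, with the caps fully used.
- New-onset rates p on drug.
- Every patient below 30 at baseline counts as an event. Under the present window this is automatic when the Visit 1 value is below 30 and dosing starts that day.

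**Share s below 30 at baseline**
- Very high albuminuria is about 90% of patients; 10% of those at eGFR ≥60 is 9% of all. The other 91% lie over 25 to <60, a span of 35 units of which 5 are below 30.
- s = 0.91 × 5/35 = 0.130, or 754 of 5800.
- With nobody at ≥60: s = 5/35 = 0.143, or about 829 of 5800.
- In the 25 to <45 stratum: 5/20 = 0.25, so the difference there falls by a quarter.

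**Dilution**
- Observed rate = s + (1 − s)p.
- Observed difference = (1 − s)(p₁ − p₀), whatever p₀ and p₁ are.

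At assumed new-onset rates of 20% and 25% (difference 5.0 points, ratio 1.25):

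| s | Observed rates | Difference (points) | Ratio |
|---|---|---|---|
| 5% | 24.0% vs 28.75% | 4.75 | 1.20 |
| 13.0% | 30.4% vs 34.75% | 4.35 | 1.14 |
| 14.3% | 31.4% vs 35.7% | 4.29 | 1.14 |
| 20% | 36.0% vs 40.0% | 4.00 | 1.11 |

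**Test statistic.** The continuity-corrected chi-square is N(|ad − bc| − N/2)² / [(a+b)(c+d)n₁n₂], where a and b are events, c and d non-events, and N = n₁ + n₂. Counts are rounded to whole patients.
- s = 13.0%, 20% vs 25%: as planned, 882 vs 1008 of 2900 gives 12.3. With baseline ≥30, n = 2900 × 0.87 = 2523 per arm, and 505 vs 631 gives 17.8. Both are clearly significant.
- s = 14.3%, same rates: 11.9 as planned against 17.7 with n = 2486.
- s = 13.0%, 10% vs 12.5%: as planned, 629 vs 692 of 2900 (21.7% vs 23.9%) gives 3.8, p = 0.052. With baseline ≥30, 252 vs 315 of 2523 gives 7.6, p = 0.006.

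**The Visit 1 window alone.** It adds a patient only if the Visit 1 value is below 30 and no later on-drug value is. If r is the fraction of baseline <30 patients who are never below 30 again, the increment per arm is s × r, or 1.3 to 1.4 points for each 10% in r. The documents do not give r.

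**The case against.** The strongest points on the other side are these.

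- **The window has little shown effect by itself.** This stands for eGFR <30. Most of the size comes from the missing baseline condition, and restricting to baseline ≥30 makes the window change redundant where Visit 1 is the baseline. The window still governs the potassium thresholds, even if the effect there is probably small.
- **The smaller difference is a change of denominator.** 4.35% of 2900 and 5.0% of 2523 are both about 126 excess patients, so the planned table gives the correct excess per treated patient. This is true. The diluted ratio, the weaker test and the treatment-emergent label on pre-existing cases remain.
- **The by-visit table exposes the problem.** A Visit 1 row would show the pre-existing cases, and subtracting it from the overall count recovers new onset for same-day starters. That helps, but it gives no test or interval. The by-stratum table helps less, because the 25 to <45 stratum mixes patients above and below 30.
- **New decline is already measured.** SAP 6.4.2 also lists relative eGFR falls of 30%, 40%, 50% and 57% or more, and protocol and SAP agree on absolute eGFR <30 as a status measure. A status measure is legitimate, but then it should not be tested as treatment-emergent.
- **The change of label was documented.** SAP 7.3 records an alignment of the treatment-emergent and on-treatment terms. It does not address the Visit 1 sample.
- **The 10% vs 12.5% example is selective.** The sample size assumes 12% placebo renal events a year, about 1 − exp(−0.24) = 21% over two years, and a 40% fall from any eGFR below 50 ends below 30. A 10% new-onset rate may therefore be low, and little should rest on that p-value moving across 0.05 in an explorative test.

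**Conclusion.** The concern holds. As written, the SAP counts pre-drug status as an on-drug event in two ways: through the date-based window and through the unconditional eGFR <30 threshold. The reported eGFR <30 difference falls by the share of patients already below 30, whatever the new-onset rates. That share is not in the documents; 13% to 14% follows from an assumed uniform spread, and 5% to 20% would shrink a 5-point difference to between 4.75 and 4.0 points. At 20% versus 25% the conclusion of the test would not change; at lower rates it could. The consequence is confined to explorative safety output, favours neither arm and leaves the primary and secondary endpoints untouched. It should be corrected because a stated rule gives a wrong classification and the planned overall test and interval do not repair it.

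**What to change.** 1. **SAP 4.5.3:** exclude the record used as baseline, that is, the pre-dose Visit 1 sample, from *Any treatment-emergent*. The baseline flag is enough; no clock times are needed.
2. **SAP 6.4.2:** base the between-arm comparison of eGFR <30 on patients with baseline eGFR ≥30. Show counts for patients with baseline eGFR <30, and for those with baseline missing, in separate rows so that no patient in the safety analysis set drops out of the display.

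The cost is two wording changes and one or two table rows, from data already held. The denominator of this one comparison shrinks by the assumed 13% to 14%, to about 2523 or 2486 instead of 2900 per arm. Precision is not lost. At 20% versus 25%, the Wald 95% half-width 1.96√[p₀(1 − p₀)/n + p₁(1 − p₁)/n] is 2.3 points with n = 2523, against 2.4 points for the planned 30.4% versus 34.75% with n = 2900.

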4.5.4 Subgroup analyses

Exploratory subgroup analysis will be performed for the primary and secondary efficacy variables. The subgroup analyses will include the randomization stratification factors. The list of key subgroups (in addition to the stratification factors) and other subgroups analysed is specified below. Analysis will include descriptive statistics, graphical display of estimated treatment effects with 95%-CIs in a forest plot and a statistical test for interaction.

Stratification factors:

- Region (North America, Latin America, Europe, Asia, Others)
- eGFR category at screening (eGFR 25 to <45, 45 to <60 and ≥ 60 mL/min/1.73m²)
- Type of albuminuria at screening (high albuminuria, very high albuminuria)

Persistent high albuminuria is defined as UACR of ≥ 30 mg/g (≥ 3.4 mg/mmol) but <300 mg/g (<33.9 mg/mmol) in 2 out of 3 first morning void samples. Persistent very high albuminuria is defined as UACR of ≥ 300 mg/g (≥ 33.9 mg/mmol) in 2 out of 3 first morning void samples.

Key subgroups (in addition to stratification factors)

- History of CVD (present, absent)
- Sex (male, female)
- Race (white, black, Asian, other)
- Age at run-in visit (<65, ≥ 65 years)
- eGFR category at baseline (eGFR <25, 25 to <45, 45 to <60 and ≥ 60 mL/min/1.73m²)
- Type of albuminuria at baseline (normalalbuminuria (UACR <30 mg/g), high albuminuria, very high albuminuria)
- Baseline serum potassium value (\leq median and $>$ median in the FAS)
- UACR at baseline (\leq median and $>$ median in the FAS)
- Systolic blood pressure at baseline (\leq median and $>$ median in the FAS)
- Baseline BMI (<30, ≥ 30 kg/m²)
- Hemoglobin A1C ($\leq 7.5\%$ / $> 7.5\%$)
- SGLT-2 inhibitors treatment at baseline (yes, no)
- GLP-1 agonists treatment at baseline (yes, no)

Other subgroups

- Baseline serum potassium value (≤ 4.5 , > 4.5 mmol/L)
- Baseline serum potassium (by quartiles in the FAS: $\leq Q1$, $> Q1$ and $\leq Q2$, $> Q2$ and $\leq Q3$, $> Q3$)
- Baseline serum potassium value (< 4.8 mmol/L, ≥ 4.8 to 5.0 mmol/L, > 5.0 mmol/L)
- Baseline hemoglobin A1C (by quartiles in the FAS: $\leq Q1$, $> Q1$ and $\leq Q2$, $> Q2$ and $\leq Q3$, $> Q3$)
- Baseline C-reactive protein (by quartiles in the FAS: $\leq Q1$, $> Q1$ and $\leq Q2$, $> Q2$ and $\leq Q3$, $> Q3$)

- Systolic blood pressure at baseline (<130 mmHg, 130 to <160 mmHg, and \geq 160 mmHg)
- Age at run-in visit (18 to 44 years, 45 to 64 years, 65 to 74 years, 75 years and over)
- Ethnicity (hispanic or latino, not hispanic or latino, not reported)
- Baseline BMI (<20, 20 to <25, 25 to <30, 30 to <35, \geq 35 kg/m²)
- Baseline weight (<60, 60 to <90, \geq 90 kg)
- eGFR at baseline 25 to < 45 ml/min/1.73m² and baseline serum potassium value >4.5 mmol/L (yes, no)
- ACEI at baseline (yes, no)
- ARB at baseline (yes, no)
- Beta-blocker at baseline (yes, no)
- Diuretic at baseline (yes, no)
- Statins at baseline (yes, no)
- Other anti-diabetic treatment at baseline: insulin and analogues (yes, no); DPP-4 inhibitors (yes, no); biguanides (yes, no); sulfonylureas (yes, no); alpha glucosidase inhibitors (yes, no); meglitinides (yes, no); thiazolidinediones (yes, no)
- Potassium supplementation at baseline (yes, no)
- Potassium lowering agents (including binders) at baseline (yes, no)
- Potency of concomitant CYP3A4 inhibitor medication at baseline (strong, weak, moderate, unclassified, none)
- Potency of concomitant CYP3A4 inducer medication at baseline (strong, weak, moderate, unclassified, none)
- Baseline waist circumference (normal [men <94cm, women <80cm], increased [men 94-102cm, women 80-88cm], substantially increased [men >102cm, women >88cm])

If the result for a subgroup cannot be calculated due to a small sample size or number of events, then this subgroup will be dropped.

Individual country analyses, e.g. for Japan, required for regulatory purposes, will be included in a country-specific study SAP.

For the safety variables

- Number of subjects with hospitalization for hyperkalemia
- Number of subjects discontinuing study drug permanently due to hyperkalemia
- Number of subjects with hospitalization for worsening of renal function
- Number of subjects discontinuing study drug permanently due to worsening of renal function

Exploratory subgroup analyses will be performed in the following selected subgroups:

- eGFR category at baseline (eGFR 25 to <45, 45 to <60 and \geq 60 mL/min/1.73m²)

- Baseline serum potassium value (≤ 4.5 , > 4.5 mmol/L)
- Anti-diabetic treatment at baseline: DPP-4 inhibitors (yes, no); GLP-1 agonists (yes, no); SGLT-2 inhibitors (yes, no)
- Potency of concomitant CYP3A4 inhibitor medication at baseline (strong, weak, moderate, unclassified, none)

